#### *Research with facilitators and costing*

To ensure confidentiality the data on facilitators (both costing and delivery) will be kept away from the implementing organisation (Project Empower) until the data's anonymity is secure. Research assistants will report to the PI and provide the PI with data, who will ensure anonymity for the participants before the data is shared more widely within the project team. Facilitators will be promised that this information will not be provided to Project Empower in any way that could lead to facilitator's being identified nor be linked to their job.

#### *In-depth interviews, Participant observation and PhotoVoice*

To ensure participant confidentiality, any notes and audio recordings will be written up as anonymised data, with false names. During PhotoVoice a key component is ensuring anonymity of photos, through strategies such as not taking photos of faces, this will be discussed extensively with participants during the study (Appendix 32).

All field researchers (data collectors and facilitators) will be required to sign an Agreement of Confidentiality (Appendix 5). This agreement will bind them to uphold the confidentiality of all information encountered during the research.

All computers and study databases will have password authentication for access. Data from the trial will be anonymously processed and written into a study report and also published in peer reviewed journals. Study data, informed consents and confidentiality agreements will be kept at the HEARD's & MRC offices for a period of 5 years after writing the findings of the trial.

### **9.5 Potential risks related to the interviews**

Participants will be guaranteed that the information will be kept confidential. At the point of data analysis information will be anonymously processed in order to minimise the possibility of data, in particular disclosed illegal behaviour, to be linked back to individual participants. Further we will not collect sufficient information about any act in the questionnaire to enable a prosecution of any crime.

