### **7.5 Inclusion criteria**

Participants must be normally resident in an informal settlement, aged 18-30 years, not in formal employment, able to communicate in the main languages of the study (isiXhosa or isiZulu) and not suffering from a mental deficit (learning difficulty, mental illness or substance abuse) which would impair their ability to consent to participation in the trial.

Our age grouping is based on the requirement that participants provide informed consent, those under 18 cannot do so and require parental consent to participate, which may be challenging in informal settlements where young people do not live with their parents. Our pilot data suggests that an upper-age limit of 30 is reasonable; while the majority of participants are under 25, a significant minority were older and faced similar life challenges.

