## **9.2 Informed Consent**

All research participants will be asked to give written informed consent (consent forms in Appendix 06) before participating. Adequate information about the trial will be given to prospective participants prior to giving consent. They will be informed of the purpose of the

trial, procedures involved, risk and benefits of the trial and their rights as participants. Prospective participants will be informed that they do not have to participate in the trial unless they are happy with the trial procedures and understand what the trial is about. All participants will be told that participation is voluntary, that they may withdraw at any stage, skip any question in the research and that there will be no adverse effects on them should they decide not to participate.

For the success of the project we require all research participants to agree in principle to multiple interviews (i.e. baseline, 12m and 24m) - although they may change their mind. For this reason we propose to stagger the consent process over a period of time and ensure that no interviews are conducted on the first day that a person has been introduced to the idea of the research.

The participant information leaflets consent forms are written in simple English, however to enhance understanding, the explanation and discussion may be in isiZulu, isiXhosa or English depending on the participant's language preference. A researcher will be present throughout the informed consent process and will clarify any questions the participants are not clear about.

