### **9.4 Confidentiality & anonymity**

All participants will be assured that the information they provide in the trial will be handled confidentially and findings reported with complete anonymity. Once the data has been uploaded and sent to the MRC and HEARD it will be stored in password protected systems.

This trial will use self-administered cell phones for collecting the quantitative data. Electronic handheld devices have been used by the MRC Gender and Health Research Unit in previous research with young and adult men and women in the Eastern Cape, KwaZulu-Natal and Gauteng, and with great success with both literate and illiterate people.

Use of cell phones in this trial will ensure anonymity of information given by participants as they will not write their names in the cell phone. Participants will have unique study codes that will not be linked to their names and thus their responses will not be traceable back to them. Using cell phones will allow us to collect data anonymously and this will therefore protect both researchers and participants should the latter disclose illegal activities or practices in the interviews.

However, we recognise that there are limits to confidentiality and have highlighted this in Appendix 06 – Informed Consent. Specifically, we have included the words: “If during a workshop the person running the workshop feels you may be about to provide too much information (such as an intention to harm someone else in the future) they will warn you not to reveal any further information. If you did continue to tell them about this, we may be required to report the information to the authorities (e.g. Police or Social Workers).”

We assume that this is unlikely to happen. Facilitators will be trained to stop participants in workshops before they reveal issues that may need to be reported, however there are cases where unsolicited reports that may emerge [61] and if participants do report such activities to fieldworkers, facilitators or team members we may have to report onwards. In an unlikely event that a disclosure of incriminating information is made, the principal investigator will report this information to the ethics committee for advice and guidance. The principal

investigator and the EC will discuss the gravity of the disclosure and the course of action to be taken.

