The World Health Organisation developed guidance on safety in conduct of research in this area [62] and guidance for safe conduct of research on male perpetration of sexual violence has been developed by the Sexual Violence Research Initiative (Sexual Violence Research Initiative, forthcoming). These documents recommend that the nature of gender-based violence research be concealed from non-interviewees until after the completion of fieldwork. The risk of retribution against men disclosing perpetration is guarded against by using self-completion for disclosure of acts that are socially stigmatised or involve the most severe forms of violence. This is implemented here. In the few cases where self-completion cannot be implemented due to illiteracy, fieldworkers will be trained to keep information confidential. The third area of risk relates to psychological distress experienced by participants. Research from diverse global settings (such as Nicaragua and South Africa) has shown that women victims of violence are saddened by talking about their exposure to violence but overwhelmingly they welcome a chance to talk and many describe the research interview as a life changing occurrence, further men who have raped can find discussing it in interviews makes them realise that it was wrong [53, 63-65]. Thus research has shown that if these guidelines are followed there are minimal risks attached to survey research on gender-based violence [63, 66]. The present study has included the guidance from these documents in its design. However, in cases where participants demonstrate distress or report being emotionally impacted by the research questions or intervention, they will be provided professional support as explained below.

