2.4.2. Integrity of data

Data was through self-completed questionnaires on cellphones, in either English, Zulu or Xhosa. The questionnaire had in-built skip patterns and logic checks. Data automatically uploaded to a server and was

downloaded regularly. At 24 months, audio (ACASI) was used to improve understanding by participants. Range and logic checks will be performed on data before analysis.

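### The protocol guarantees confidentiality and binds data collectors to it, yet allows onward reporting of what they are told; the consent wording it reproduces states that limit only for workshops

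*Protocol*

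**What the plan says.** Five statements in the protocol bear on this.

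- **Section 9.5**, on risks related to the interviews, gives the promise: "Participants will be guaranteed that the information will be kept confidential". No exception is attached. The same paragraph adds that the questionnaire will not hold enough detail about any act to support a prosecution.
- **Section 9.4** opens in similar terms: "All participants will be assured that the information they provide in the trial will be handled confidentially". Under its sub-heading on in-depth interviews, observation and PhotoVoice, it also requires data collectors and facilitators to sign an agreement covering all information they meet during the research. No exception is stated there either.
- **Section 9.4** also accepts that confidentiality has limits and says that Appendix 06 highlights them. It reproduces the words used, which begin: "If during a workshop the person running the workshop feels you may be about to provide too much information". They give an intention to harm someone in future as the example, and warn that a report to the authorities may be required.
- **Section 9.4** then gives the working rule: "if participants do report such activities to fieldworkers, facilitators or team members we may have to report onwards". This follows a remark that unsolicited reports can arise. Such events are called unlikely, and the principal investigator takes them to the ethics committee for advice.
- **Section 9.6** covers people who cannot complete the questionnaire themselves: "In the few cases where self-completion cannot be implemented due to illiteracy, fieldworkers will be trained to keep information confidential".

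**The concern.** The trial asks men about physical and sexual violence they have committed and women about violence done to them. Before answering, participants need to know who may learn what they say and when it may be passed on. Here they are promised confidentiality without qualification, while staff work under a rule that allows reporting. The limit that the protocol shows as disclosed is also narrower than that rule.

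Two things are at stake. The first is whether consent is truthful: a participant may rely on a promise that the study may not be able to keep. The second is the protection of anyone who tells a fieldworker about an illegal act outside a workshop without having been warned. Staff are exposed as well, because they sign an agreement without exceptions and are then subject to a rule that makes one.

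**Working it through.** No arithmetic underlies this point, so the check is a comparison of the protocol's statements on three questions.

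**1. Do the promise and the reporting rule agree?**

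| Source | Who or what is covered | Exception stated? |
|---|---|---|
| 9.5, guarantee | Information given by participants | No |
| 9.4, opening assurance | Information given by all participants | No |
| 9.4, staff agreement | All information met by data collectors and facilitators | No |
| 9.4, reporting rule | Illegal acts reported to fieldworkers, facilitators or team members | This is the exception |
| 9.6, assisted completion | Information from those who cannot self-complete | No |

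The reporting rule names fieldworkers. The guarantee, the agreement and the assisted-completion rule cover the same people without exception. The sections do not say which rule prevails. The statements therefore conflict for any illegal act told to a fieldworker.

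**2. Does the disclosed limit match the rule?**

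- Reporting rule: facilitators, fieldworkers and team members, with no restriction on setting.
- Consent wording reproduced in 9.4: what is said during a workshop to the person running it.
- Left out of the reproduced wording: anything said to a fieldworker or team member, and anything said to a facilitator outside a workshop.

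The gap is widest in the control arm. Section 7.7 puts 17 clusters in each arm, so 17 of 34 clusters, or half, are controls. Section 9.0 gives them the intervention only after the last evaluation at 24 months. Throughout follow-up, the reproduced limit refers to sessions they do not attend, whereas fieldworkers survey them at baseline, 12 and 24 months.

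**3. Which rule governs assisted questionnaire answers?**

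Section 9.6 says that self-completion is what guards men who disclose perpetration against retribution, and then allows for a few cases in which it cannot be used. For those cases it relies on fieldworkers keeping the information confidential. Section 9.4 neither includes these answers in the reporting rule nor exempts them.

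**The case against.** The best defence is that the rules have different subjects. Section 9.4 speaks of unsolicited reports, whereas questionnaire answers are solicited and fall under 9.6, which promises confidentiality. Section 9.5 limits the detail collected, and disclosures go to the ethics committee before any action. In the in-depth interviews, observation and PhotoVoice, 9.5 also provides a spoken warning.

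This is a sensible reading, and it should prevent anyone from saying that survey answers *will* be reported. It does not remove the conflict:

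- The protocol does not draw the solicited/unsolicited line as a rule, and an unsolicited remark to a fieldworker is still covered by the 9.5 guarantee.
- Limiting the questionnaire's detail does not limit what a participant says aloud.
- Ethics committee advice comes after the disclosure and does not inform the participant beforehand.
- The spoken warning belongs to a sub-study of 40 people drawn from two intervention clusters (7.14), not to the survey.

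Several stronger readings are tempting, but the documents do not support them.

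- *The consent form states no other limit.* Appendix 06 is not in the documents. Only the excerpt can be judged.
- *Non-readers must speak their answers about violence to staff.* Section 9.6 implies that fieldworkers learn these answers but does not describe how. It speaks of few cases, and 7.9 reports that almost all pilot participants could complete the questionnaire alone. No number of non-readers is given, so any headcount would be assumed.
- *The warning is in a language participants cannot read.* Section 9.2 on consent does say "The participant information leaflets consent forms are written in simple English", and 7.5 requires only that people be "able to communicate in the main languages of the study (isiXhosa or isiZulu"). But 9.2 goes on to allow explanation and discussion in isiZulu or isiXhosa, with a researcher present.
- *Speaking answers aloud was avoidable from the start.* SAP section 2.4.2 says only that "At 24 months, audio (ACASI) was used to improve understanding by participants". The stated purpose is understanding rather than privacy, and availability at baseline is not shown.
- *The primary result is biased.* Fear of reporting could lead some people to deny acts, but the documents give no figure for this and no reason why it would differ by arm. The SAP outcomes are at 24 months.

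**Conclusion.** The concern holds as a contradiction in participant protection. An unqualified guarantee and an unqualified staff agreement stand beside a rule that allows onward reporting of what fieldworkers are told. The reproduced consent wording discloses that limit for workshops only, and the status of assisted answers is left open.

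Its reach can be stated only in part. The guarantee and the opening assurance apply to all participants, and the mismatch with the workshop wording is plainest for the 17 control clusters. That figure describes who receives a limit of no relevance to their trial contact before 24 months; it does not count people harmed. The number who would need help with the questionnaire is unknown.

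The conclusion rests on one assumption: that nothing elsewhere in Appendix 06 states the limit for fieldworkers and team members. If it does, the consent gap closes, but the conflict among 9.4, 9.5 and 9.6 remains. No effect on the treatment comparison is shown, and none is claimed.

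**What to change.** 1. Reconcile sections 9.4 (including the staff agreement), 9.5 and 9.6 so that they state one rule on confidentiality and its limit.
2. In 9.5, replace the guarantee with confidentiality subject to that limit, and make the staff agreement in Appendix 05 consistent with it.
3. In Appendix 06, extend the limit from workshops to any contact with a facilitator, fieldworker or team member, unless the full form already does so.
4. Take ethics committee advice, then state whether assisted questionnaire answers fall under the reporting rule. The documents do not settle the legal position, so an exemption should not simply be declared.

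IsiZulu and isiXhosa consent forms, and audio self-completion before 24 months, are optional improvements; the finding does not depend on them.

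The cost is a wording amendment and ethics review. A less absolute promise may slightly reduce willingness to enrol or to disclose. In return, participants are told the truth about confidentiality before they answer.

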#### *Research with facilitators*

As facilitators are employees of the implementing agency, there is significant risk to them in their professional life. We will ensure that no data is seen by the implementing agency on the experiences of facilitators until it has been full anonymized.

#### *Indepth Interviews, Participant observation and PhotoVoice*

As participants build up relationships with the research team over the course of participant observation and PhotoVoice sessions, there is a risk that they will disclose information that is illegal. As with other studies where the team have undertaken qualitative research on illegal behaviours [20, 30, 61] we will make participants aware when they start telling stories which we may be forced to tell others (e.g. social workers, police) to reduce this from happening. Any instances where we may be forced to compromise the privacy of will be discussed with ethics committees beforehand [61].

## **9.6 Harm due to the study**

We will collect data on potential risks related to the study. It is a sad fact in South Africa that large randomised controlled trials always experience deaths of study participants. It is critical that these are investigated and shown to be not study related. For example, during the pilot study of 232 participants who we intended to follow for a year there were three deaths and one participant went to jail. Similarly in the first Stepping Stones evaluation there were 16 deaths in 2800 people followed for 2 years. We investigated all these and found none to be study related. The investigation of study participant deaths will be conducted by the counsellor. At an appropriate time, he or she will be asked to visit the family (or friends if no family are available) to collect information on the circumstances of the death. A report will be sent to the ethics committee. We will inform participants that if there should be a death that they learn of we must be informed and we may also learn of deaths when conducting follow up interviews. We are not administering medication to participants and the basic interventions are known to be safe (Stepping Stones has been used with 10s of thousands of participants globally) so we do not anticipate any study related deaths.

Given that this is a study on violence we will also undertake investigations for any reported hospitalisations or escalating violence that are reported to study staff. The counsellor will at an appropriate time collect information on the causes of hospitalisation or escalation of violence and provide a written report that will be forwarded to the ethics committee for their review.

This research includes a number of sensitive topics. It has been well established that there is a potential for harm to participants in research on gender-based violence. The most important concerns relate to the risk of re-victimisation of women for engagement in the study; the risk of retribution against perpetrators disclosing in these studies; and the risk of psychological distress to participants through being asked to re-remember traumatic events.

The World Health Organisation developed guidance on safety in conduct of research in this area [62] and guidance for safe conduct of research on male perpetration of sexual violence has been developed by the Sexual Violence Research Initiative (Sexual Violence Research Initiative, forthcoming). These documents recommend that the nature of gender-based violence research be concealed from non-interviewees until after the completion of fieldwork. The risk of retribution against men disclosing perpetration is guarded against by using self-completion for disclosure of acts that are socially stigmatised or involve the most severe forms of violence. This is implemented here. In the few cases where self-completion cannot be implemented due to illiteracy, fieldworkers will be trained to keep information confidential. The third area of risk relates to psychological distress experienced by participants. Research from diverse global settings (such as Nicaragua and South Africa) has shown that women victims of violence are saddened by talking about their exposure to violence but overwhelmingly they welcome a chance to talk and many describe the research interview as a life changing occurrence, further men who have raped can find discussing it in interviews makes them realise that it was wrong [53, 63-65]. Thus research has shown that if these guidelines are followed there are minimal risks attached to survey research on gender-based violence [63, 66]. The present study has included the guidance from these documents in its design. However, in cases where participants demonstrate distress or report being emotionally impacted by the research questions or intervention, they will be provided professional support as explained below.

## **9.7 Intervention Challenges**

In the pilot a number of women described having arguments with their main male partners about their participation in the intervention (rather than research). This was related to the fact that they had been unable to discuss openly with their partner their participation. To minimise potential risk and harm participants may face we have added in additional guidance and focused discussion with facilitators around supporting participants to actively think through discussing their participation with partners or family members and the potential benefits and risks of this.

### **9.8 Referral**

Project Empower will employ a counsellor who can be accessed by all participants via a cell phone (please call me messages) and will be able to provide support over the period of the study. If referral to another agency is required (e.g. to a Thuthuzela Care Centre after rape) the counsellor will be able to facilitate this. This will be given to all study participants. The decision to use Project Empower is that participants will have greater contact with Project Empower over the study and will be more likely to contact Project Empower – rather than HEARD – in the case of concerns about their wellbeing.

All participants will be informed that should they feel they have been upset or affected negatively by the research questions or content of the intervention, they are welcome to speak to the study counsellor at no cost to them. All participants will be provided with the study counsellor's number for them to contact. The facilitators and research assistants will be trained to identify participants who are visibly distressed during the interviews or intervention sessions and with their permission refer them to the trial counsellor.

